#### **6.2.3 Exploratory Outcome Measures**

• To detect the expression level of EGFR in tumor pathological tissues of subjects;

#### **6.3** Drug tolerability assessment

#### **6.3.1 Selection of starting dose**

In the first-in-human Phase I clinical trial, the preliminary starting dose of MRG003 was set at 0.1 mg/kg administered once every 3 weeks (Q3W). According to the multiple dose GLP safety evaluation study of MRG003 in cynomolgus monkeys, the doses of 1, 3 and 6 mg/kg were administered once every three weeks for 4 doses (Q3W4), and the study results determined that 6 mg/kg was the HNSTD in cynomolgus monkeys. According to the comprehensive evaluation of the first human dose of ADC drugs by US FDA (Saber-2015), it is considered that the dose 1/6 of the highest non-severely toxic dose (HNSTD) calculated by body surface area in cynomolgus monkeys is selected as the first in human (FIH) dose, which is an acceptable phase I clinical starting dose under the condition of balanced safety and efficacy. Therefore, it is speculated that 0.3 mg/kg MRG003 can be used as the starting dose in human clinical trials. However, with reference to the US FDA Guidelines for Estimating the Maximum Safe Starting Dose for the First Time in Human,

the calculated starting dose of MRG003 in human is 0.2 mg/kg. For safer consideration, the initial starting dose of MRG003 can be set at 0.1 mg/kg.

#### **6.3.2** Selection of maximum dose

581

582

583

584

585

586587

588

589

590

591

592

593 594

595

596

597598

599

600

601 602

603

604

605

606

607

608

609

610

611

612 613

614

615

The maximum dose that may be achieved during the dose escalation phase is 3.0 mg/kg. According to several clinical trials of vcMMAE-based ADC drugs for different targets in Europe and the United States, DLT is usually caused by the toxicity of MMAE, and MTD is generally occurred at the dose of 1.8 – 2.4 mg/kg.

#### **6.3.3 Dose Escalation Scheme**

MRG003 will be assessed for dose-limiting toxicity during the first treatment cycle of Phase Ia. Intravenous drip of a certain dose of MRG003 was given to the patient for recuperation for 3 weeks, which was considered as 1 treatment cycle. In the drug tolerance study, the modified accelerated titration dose escalation method was followed for the early two dose groups (0.1, 0.3 mg/kg), and the standard 3 + 3 (modified Fibonacci method) dose escalation method was followed for the subsequent dose groups (0.6, 1.0, 1.5, 2.0, 2.5, 3.0 mg/kg). The escalated doses and the number of subjects are presented in Table 2. In the 0.1 mg/kg and 0.3 mg/kg dose periods, only 1 subject was required. If a subject experiences an adverse reaction at 0.1 mg/kg and meets the DLT criteria, the tolerance test protocol will be converted to the 3 + 3 method (i.e., add another 2 subjects in the 0.1 mg/kg dose group); if the adverse reaction of a subject does not meet the DLT criteria, the tolerance test can enter the next dose group. Doses of 0.6 mg/kg and higher were escalated by the 3 + 3 method. In any dose group, if none of the 3 subjects experienced DLT at the end of treatment cycle, the tolerance test could enter the next higher dose group; if 1 of the 3 subjects experienced DLT at the end of treatment cycle, another 3 subjects were included in this dose group. If none of the additional 3 subjects experienced DLT, the tolerance test could enter the next dose group. If 2 or more of 3 or 6 subjects in a dose group experienced DLT, dose escalation was stopped and the previous low dose group was the maximum tolerated dose (MTD). To find a more accurate MTD, an intermediate dose group may be added to the preset dose based on available safety and PK data. Dose escalation plan see Table 2. If the MTD is not observed in the above dose groups, dose escalation will continue in a 3 + 3 manner by escalating no more than 20% of the previous dose level until the MTD is reached. In the 3 + 3 escalation method, each subject received only one corresponding dose. The next escalating dose was not entered until the end of each dose observation. Trials with more than two dose groups could not be performed simultaneously. See Table 3 for the judgment principles of MTD or RP2D.

Table 2: Dose escalation scheme and number of subjects

Dose Group	1	2	3	4	5	6	7	8	9 above
Escalation		200%	100%	67%	50%	33%	25%	20%	< 20%
Dose (mg/kg)	0.1	0.3	0.6	1.0	1.5	2.0	2.5	3.0	TBD
Number of people	1	1	3 + 3	3 + 3	3 + 3	3 + 3	3 + 3	3 + 3	3 + 3

Tolerance		$\sqrt{}$	$\sqrt{}$	$\sqrt{}$	$\sqrt{}$	$\sqrt{}$	$\checkmark$	$\checkmark$	$\sqrt{}$
Kinetics	V	$\checkmark$	$\checkmark$		$\checkmark$		$\checkmark$	$\checkmark$	$\sqrt{}$

### Table 3: 3 + 3 dose escalation method and MTD and RP2D determination principles

Number of subjects meeting DLT criteria at a dose	Dose escalation principle
No subjects met the criteria for DLT	Three new subjects entered the next dose phase
3 subjects 2 or 3 met criteria for DLT	The tolerability trial was terminated. The dose of the former group was the MTD. If only 3 subjects are tested in the previous dose group, another 3 new subjects shall be selected to enter the previous dose group for the study to explore MTD/RP2D dose.
3 subjects – 1 met criteria for DLT	An additional 3 new subjects should be re-tested at this dose stage.  If no newly selected 3 patients meet the criteria for DLT, another 3 patients can be selected to enter the dose phase for the trial.  If 1 or more of the newly selected 3 patients meet the criteria for DLT, the tolerance test is terminated, and the dose of the previous group is the MTD. If only 3 subjects are tested in the previous dose group, another 3 new subjects shall be selected to be tested in the previous dose group (0/6 or 1/6).
The RP2D was selected with reference to the MTD and the following information available: low-grade AEs, AEs occurring in subsequent treatment cycles, PK, and efficacy data.	At least 6 subjects were treated at the MTD/RP2D. The MTD/RP2D dose will be assessed by the Safety Monitoring Committee (SMC).

#### 6.3.4 Dose-limiting toxicity, maximum tolerated dose and recommended phase II dose

#### 6.3.4.1 Judgment criteria for dose limiting toxicity (DLT)

A DLT was defined as an AE (except allergic reaction) or abnormal laboratory value not related to disease progression, or concomitant disease, or concomitant medication, and met any of the following criteria in the DLT table (Table 4). Adverse events will be assessed according to CTCAE v4.03. Any subject who fails to complete the 21-day observation period for reasons other than DLT will be considered as not evaluable for DLT, and another subject in the same dose group should be added.

Table 4: Judgment criteria for DLT according to CTCAE 4.03 classification

Toxicity	Any of the following criteria
Blood	Grade 4 neutropenia lasting > 7 consecutive days
	Grade 3 thrombocytopenia lasting > 7 consecutive days
	Grade 4 thrombocytopenia
	Grade 3 febrile neutropenia (granulocytes < 1.0 × 109/L, body temperature ≥ 38.5°C) requiring antibiotics
Kidney	Serum creatinine greater than 3 times the upper limit of normal for > 7 consecutive days
	≥ Grade 3: Blood creatinine increased
Liver	Total bilirubin greater than 3 times the upper limit of normal for > 7 consecutive days
	≥ Grade 3 total bilirubin elevation
	Grade 3 AST or ALT elevation lasting > 7 consecutive days
	Grade 4 elevated aspartate aminotransferase (AST) or alanine aminotransferase (ALT)
Pancreas	Symptomatic amylase or lipase abnormalities ≥ CTCAE Grade 3
	Asymptomatic ≥ CTCAE Grade 3 amylase or lipase abnormality lasting longer than 7 days
Cardiovascular system	≥ Grade 3
Eye	≥ Grade 3
Skin	Grade 3 or 4 skin toxicities that remain uncontrolled despite symptomatic treatment
Nervous system	≥ Grade 3: Neurologic toxicity
Other Adverse Events	≥ Grade 3: Uncontrolled vomiting and nausea despite the use of antiemetic doses
	≥ Grade 3: Uncontrolled diarrhea despite the subject's use of antidiarrheal medication
	Treatment delay of > 14 days due to unresolved toxicity that does not resolve to Grade 1 or baseline
	Other ≥ Grade 3 AE

Any other unacceptable toxicity as determined jointly by the investigator and the sponsor's medical monitor

Note: 3 kinds of adverse reactions are not regarded as criteria for DLT judgment:  $\geq$  Grade 3 anemia (unless there is indirect relationship with MRG003);  $\geq$  Grade 3 lymphocytopenia (unless there is clinical significance);  $\geq$  Grade 3 hypercholesterolemia or hypertriglyceridemia.

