#### 6.1 Total trial design

This study is designed as two parts: the first part of Phase Ia dose escalation study is a single-center, non-randomized, single-arm, open-label clinical trial for the first time in human to determine the maximum tolerated dose (MTD) or recommended Phase II dose (RP2D) of MRG003 in patients with advanced solid tumors; the second part of Phase Ib dose expansion study is a multi-center, non-randomized, single-arm, open-label clinical trial to preliminarily evaluate the efficacy of MRG003 in patients with advanced colorectal cancer, head and neck squamous cell carcinoma and nasopharyngeal carcinoma. Both parts will evaluate the safety, tolerability, immunogenicity and kinetics of MRG003 in human.

In the Ia study phase, the early two low doses followed a modified accelerated titration dose escalation design, and the subsequent six doses followed a standard 3 + 3 dose escalation design. MRG003 was administered by intravenous drip on the first day of every three weeks (Q3W). Dose-limiting toxicity (DLT) was assessed on Day 21 (Days 1 to 21) of the first dose administration. The MTD is defined as the dose at which 0/6 or 1/6 subjects in the current dose group experience a DLT, provided that  $\geq 33\%$  of subjects experience a DLT at the next higher dose (i.e., 2/3 or 2/6). Even if the MTD has been reached, the selection of the RP2D still requires reference to the MTD and the following available information: low-grade AEs, AEs occurring in subsequent treatment cycles, PK and efficacy data. In the dose escalation phase, if the MTD cannot be determined based on the planned dose (e.g., further dose escalation does not result in a significant increase in exposure), the RP2D will evaluate the available safety, PK, and efficacy data via a dose escalation teleconference or teleconference to determine the dose for the dose expansion phase. Once the MTD is determined through a safety assessment meeting, approximately 3 new subjects may be enrolled at the previous low dose level to collect additional PK and safety data upon discussion between the sponsor and the site. At least 6 subjects will be treated at the MTD/RP2D. The MTD/RP2D was selected as the dose for further study in Part Ib.

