#### 8.1.6 Administration method and administration period

MRG003 will be administered as an intravenous infusion on Day 1 of each cycle.

Each MRG003 dosing cycle is every 3 weeks (Q3W). Each subject received up to 8 dosing cycles throughout the study.

Prior to the start of each dosing cycle, subjects must meet the following conditions to receive intravenous infusion of MRG003:

- Neutrophil count  $\geq 1.5 \times 10^9/L$  and platelet count  $\geq 75 \times 10^9/L$ . Supportive therapy was allowed to improve the subject's hematologic condition (except prior to the first dose).
- Adverse reactions related to study drug must have improved to baseline or CTCAE v4.03 grade ≤ 1. For adverse reactions that do not result in fatal organ damage, such as hair loss, the investigator may decide whether the drug can be administered to the subject.

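### The treatment-delay DLT criterion in Table 4 cannot be met before Day 37, but DLTs are assessed on Days 1 to 21 and no rule makes the cohort wait

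*Protocol*

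**What the plan says.** Table 4 in Protocol Section 6.3.4.1 lists as a DLT: "Treatment delay of > 14 days due to unresolved toxicity that does not resolve to Grade 1 or baseline".

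The window and the decision rule are set elsewhere:

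- Section 6.1: "Dose-limiting toxicity (DLT) was assessed on Day 21 (Days 1 to 21) of the first dose administration". Section 9.5, item 3, restricts DLT recording to Cycle 1. Sections 6.2.1 and 14.4.3.1 define the Phase Ia primary outcome over the first cycle.
- Section 6.3.3: "if none of the 3 subjects experienced DLT at the end of treatment cycle, the tolerance test could enter the next higher dose group". For a cohort without a DLT, Table 3 says: "Three new subjects entered the next dose phase".
- The only waiting rule, also in Section 6.3.3: "The next escalating dose was not entered until the end of each dose observation".
- Evaluability, Section 6.3.4.1: "Any subject who fails to complete the 21-day observation period for reasons other than DLT will be considered as not evaluable for DLT".
- Re-dosing, Section 8.1.6: "Adverse reactions related to study drug must have improved to baseline or CTCAE v4.03 grade ≤ 1". Neutrophils must be at least 1.5 × 10⁹/L and platelets at least 75 × 10⁹/L. The investigator may dose through reactions that do not cause fatal organ damage.
- Section 8.2 withdraws a subject whose dose is delayed by more than 3 weeks.

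**The concern.** A delay criterion needs a dose that can be delayed. With one infusion per cycle, that is the Cycle 2 dose, which falls due after the DLT window has closed. A subject held on Day 22 has completed 21 days, so the evaluability rule does not remove that subject, and no Table 4 criterion has yet been met through the delay. Nothing in the protocol marks the subject as pending, defers the cohort decision, or says how a DLT confirmed on Day 37 changes a count already acted on.

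The DLT count is the Phase Ia primary outcome and drives every 3+3 step of a first-in-human trial. A missed case can only make a dose look safer:

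- **One delay-only subject in three, no other DLT:** the count is 0/3 (escalate) instead of 1/3 (add three).
- **One delay-only subject and one other DLT in three:** the count is 1/3 instead of 2/3 (stop). Three more subjects are treated at the same dose; this is not immediate escalation.

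Duration criteria have a smaller version of the gap. A Table 4 line that requires more than 7 consecutive days can still be open on Day 21.

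**Working it through.** **Dates.** Inputs: one infusion on Day 1 of each cycle (Section 8.1.6), a 3-week cycle (Section 6.3.3) and the Table 4 delay of more than 14 days.

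- Cycle 1 covers Days 1 to 21, which reproduces the window stated in Section 6.1.
- Dose 2 is due on Day 1 + 21 = Day 22.
- A delay of exactly 14 days is Day 22 + 14 = Day 36.
- A delay of more than 14 days is first met on Day 22 + 15 = Day 37, which is 37 − 21 = 16 days after the window closes.
- A 3-week delay is Day 22 + 21 = Day 43. Days 37 to 43 are thus a permitted delay that meets the criterion outside its window.

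**Can staggered dosing rescue it?** Suppose the last subject of the cohort is dosed *d* days after the held subject. That subject's Day 21 is the held subject's Day 21 + *d*. Reaching Day 37 needs *d* ≥ 16, or *d* ≥ 15 if the decision is taken on the last subject's Day 22. Section 6.3.3 sets no such spacing, and the Days 1 to 21 wording would still not cover the event.

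**Duration criteria of more than 7 days.** Onset on Day 14 gives Days 14 to 21 = 8 days, so the criterion is met. Onset on Day 15 gives Days 15 to 21 = 7 days, so it is still open. This matters for Grade 4 neutropenia, Grade 3 thrombocytopenia, Grade 3 AST/ALT and asymptomatic amylase or lipase. Creatinine and bilirubin also have a Grade 3 line without a duration.

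**Consequence, given one delay-only subject in three and no other DLT.** Correct counting adds three subjects, and any DLT among them stops escalation. With *p* the true DLT rate (assumed; the protocol gives none):

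P(stop) = 1 − (1 − *p*)³

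| *p* | P(stop) |
|---|---|
| 0.20 | 1 − 0.512 = 0.488 |
| 0.30 | 1 − 0.343 = 0.657 |
| 0.40 | 1 − 0.216 = 0.784 |

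Counted as 0/3, the cohort skips this check.

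**Unconditional illustration.** With full counting, P(escalate) = (1 − *p*)³ + 3*p*(1 − *p*)⁵. At *p* = 0.30 this is 0.343 + 0.151 = 0.494. Let *f* be the share of DLTs that are delay-only (assumed 5% or 10%), and *q* = *p*(1 − *f*) the rate seen in time.

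- **Late cases never counted:** (1 − *q*)³ + 3*q*(1 − *q*)⁵.
- **Late cases among the first three counted at the six-subject look:** (1 − *q*)³ + 3*q*(1 − *p*)²(1 − *q*)³. This is possible because three added subjects dosed on Day 22 finish on the held subject's Day 42, after Day 37.

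| *f* | *q* | Never counted | Counted at the six-subject look |
|---|---|---|---|
| 5% | 0.285 | 0.525 | 0.519 |
| 10% | 0.270 | 0.557 | 0.543 |

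Against 0.494, P(escalate) rises by 0.025 to 0.063.

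**The case against.** The best defence reads Days 1 to 21 as the window for the toxicity, with the delay as its consequence. A DLT is whatever meets a Table 4 criterion, and no sentence strikes out a listed criterion because it completes late. The Cycle 1 restriction in Section 9.5 is also loosely worded: it confines RP2D determination to Cycle 1, although Section 6.3.4.2 draws on later cycles. This reading is possible, but it settles only whether the event counts. The escalation decision is still taken at the end of the cycle, before the delay can be known.

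The other objections concern frequency, and they largely stand:

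- Most Grade 3 or higher events count through other Table 4 lines.
- Section 8.1.6 allows supportive therapy for low counts after the first dose, and Section 10.3 permits G-CSF or GM-CSF for acute toxicity. A long hold for neutropenia alone is therefore less likely.
- The Section 8.2 trigger for Grade 2 neurological disease unresolved 4 weeks after dosing (about Day 29) leads to dose reduction, not to a hold. It does show that the protocol expects persistent toxicity below the Grade 3 at which Table 4's nervous-system line begins.
- Table 6 schedules bloods before the Cycle 2 dose, so an abnormality found on Day 15 would usually be settled about one day after the window.
- The Safety Monitoring Committee oversees escalation under a charter that is not shown, and Table 4 ends with: "Any other unacceptable toxicity as determined jointly by the investigator and the sponsor's medical monitor". Both can catch cases, but only by discretion, whereas the delay criterion was written as mandatory. Using later-cycle events for the RP2D does not correct the cohort count.

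**Conclusion.** The point holds. A listed DLT criterion cannot be met inside the stated DLT window, and the protocol contains no rule that makes the cohort wait for it. Followed exactly, the protocol can escalate on 0/3 when its own criteria give 1/3.

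The affected group is narrow: mainly persistent lower-grade or haematological toxicity that the investigator will not dose through. Its frequency cannot be determined from the document. The stop probabilities of 0.49 to 0.78 apply only once such a case has occurred and rest on assumed DLT rates. The rise of about 0.03 to 0.06 in the probability of escalating rests on an assumed 30% DLT rate and an assumed 5–10% delay-only share. The dates depend on no assumption beyond the planned schedule. The conclusion concerns the protocol text; the committee charter might add a hold.

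This should be fixed: the effect is probably small, but it runs only towards under-counting toxicity in a first-in-human trial, and the correction is cheap.

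**What to change.** Amend Sections 6.1, 6.3.3, 6.3.4.1 and 9.5 (item 3) to state that:

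1. A subject whose Cycle 2 dose is held for unresolved toxicity is pending for DLT until re-dosed or through Day 36. If still not dosed by then, the subject counts as a DLT for that dose group, although this falls after Day 21.
2. A Table 4 criterion of more than 7 days with onset in Days 1 to 21 that is still open on Day 21 (onset on or after Day 15) is followed until it is met or the event resolves.
3. The cohort's escalation decision waits for all pending subjects.

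The cost is amendment wording and an occasional cohort decision delayed by about two weeks.

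### The anemia exception in the DLT note, read as written, counts Grade 3 or higher anemia caused indirectly by MRG003 and leaves out anemia caused directly; the phrase should be corrected

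*Protocol*

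**What the plan says.** Protocol 6.3.4.1 defines a DLT in two steps. The event must first pass a test of cause: "A DLT was defined as an AE (except allergic reaction) or abnormal laboratory value not related to disease progression, or concomitant disease, or concomitant medication". It must then meet a criterion in Table 4.

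Table 4 has no row for anemia. Grade 3 or higher anemia would therefore enter through the general row "Other ≥ Grade 3 AE". The note under the table blocks that route: "3 kinds of adverse reactions are not regarded as criteria for DLT judgment". Each of the three exemptions is treated differently:

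- Grade 3 or higher anemia is exempt "unless there is indirect relationship with MRG003".
- Grade 3 or higher lymphocytopenia is exempt unless clinically significant.
- Grade 3 or higher cholesterol or triglyceride elevation is exempt with no exception.

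Two other rows of Table 4 could reach a severe anemia. One is discretionary: "Any other unacceptable toxicity as determined jointly by the investigator and the sponsor's medical monitor". The other is "Treatment delay of > 14 days due to unresolved toxicity that does not resolve to Grade 1 or baseline".

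The DLT count drives escalation. Section 6.3.3 says: "If 2 or more of 3 or 6 subjects in a dose group experienced DLT, dose escalation was stopped". Table 3 gives the matching rules for 0/3, 1/3 and 2/3.

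**The concern.** An exemption for severe anemia in patients with advanced cancer is understandable, because much of it comes from the disease or earlier treatment. The natural exception is anemia related to the study drug. The note instead names only an indirect relationship. As written, it returns the weaker causal link to the DLT count and leaves the stronger one outside.

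This is an operative rule in a first-in-human trial. DLT in Cycle 1 is the Phase Ia primary outcome (6.2.1), and the MTD follows from its count (6.3.4.2). If the phrase were applied as written, a cohort with severe anemia caused directly by the drug could be recorded as free of DLT, and the next dose opened.

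**Working it through.** **What the text supports.** The protocol states no figure that depends on this phrase, so the check is mainly one of reading.

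1. *Literal reading.* Anemia is exempt unless the link is indirect. Indirect link: DLT. Direct link: exempt. No link: exempt.
2. *Threshold reading.* Anemia is exempt unless there is a link, even an indirect one. Indirect link: DLT. Direct link: DLT. No link: exempt.
3. *Does another section choose between them?* The synopsis does not restate the DLT criteria. The causality scale in 11.2.2 (Table 11) runs from definitely related to unrelated, with no direct or indirect category, so an assigned attribution cannot be mapped to the exception. No other section gives an anemia rule.
4. *Do the other Table 4 rows close the gap?* The joint-judgment row can, but only by discretion and against a note that says this event is not a criterion. The delay row is weak for anemia. DLT is assessed over Days 1 to 21 and the next dose is due on Day 22, so a delay of more than 14 days is established only after Day 22 + 14 = Day 36. Section 8.1.6 does require that "Adverse reactions related to study drug must have improved to baseline or CTCAE v4.03 grade ≤ 1" before redosing. It also permits supportive therapy to improve the blood picture after the first dose, and it sets neutrophil and platelet thresholds but none for hemoglobin.

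**What one subject does.** This follows from 6.3.3 and Table 3 alone.

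| DLTs with the anemia left out | Decision | DLTs with it counted | Decision |
|---|---|---|---|
| 0/3 | escalate | 1/3 | add 3 subjects |
| 1/3 | add 3 subjects | 2/3 | stop |
| 1/6 | escalate | 2/6 | stop |

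**Illustration on assumed rates.** The protocol gives no rates, so every input here is an assumption. Let q be the probability of any other DLT and a the probability of Grade 3 or higher anemia caused directly by the drug in Cycle 1, taken as independent. With p the DLT probability per subject,

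P(escalate) = (1−p)³ + 3p(1−p)² × (1−p)³.

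If the anemia is counted, p = 1 − (1−q)(1−a). If it is left out and no other row captures it, p = q.

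Example with q = 0.10 and a = 0.05:

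- Left out: p = 0.10, so 0.729 + 0.243 × 0.729 = 0.906.
- Counted: p = 1 − 0.90 × 0.95 = 0.145, so P(escalate) = 0.824.
- Difference: 8.2 points.

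| q | a | Left out | Counted | Difference (points) |
|---|---|---|---|---|
| 0.10 | 0.05 | 0.906 | 0.824 | 8.2 |
| 0.10 | 0.10 | 0.906 | 0.730 | 17.6 |
| 0.10 | 0.20 | 0.906 | 0.536 | 37.0 |
| 0.20 | 0.05 | 0.709 | 0.622 | 8.7 |
| 0.20 | 0.10 | 0.709 | 0.536 | 17.3 |
| 0.20 | 0.20 | 0.709 | 0.378 | 33.1 |

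Under the threshold reading, or if other rows capture every case, the difference is 0. With half of such anemias left out, it runs from 4.3 points (0.867 against 0.824, at q = 0.10, a = 0.05) to 19.4 points (0.730 against 0.536, at q = 0.10, a = 0.20).

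**The case against.** The best reply is that this is a slip of wording that nobody would apply as written. The English text has other loose renderings; for example, both INR limits in the synopsis and in 7.3 carry the same anticoagulant label. A rule that counts indirect harm and ignores direct harm makes little clinical sense, and a safety committee would be unlikely to use it. That is a fair reason to expect a small practical effect. It does not repair the text.

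A reader might also draw three stronger conclusions that the documents do not support.

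- *That the note contradicts the DLT definition.* It does not, strictly. An event must pass the test of cause and also meet Table 4, and the note narrows the second condition. It also exempts lipid elevations whatever their cause, so leaving some drug-caused events uncounted is how the note works. Only the form of the anemia exception is at fault.
- *That sites will classify the same case differently.* DLTs are recorded in Cycle 1 of Phase Ia only (9.5), Phase Ia is run at a single center (7.2), and the Safety Monitoring Committee oversees escalation (6.3.5). Divergence is possible but less likely than in a multicenter escalation.
- *That the sponsor chose to exempt anemia caused directly by the drug.* Nothing shows such an intent.

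RP2D selection also looks beyond DLTs (6.3.4.2), and anemia is graded and summarized separately (14.4.5). These are real safeguards, but they act alongside the DLT count and do not define it.

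**Conclusion.** The point holds as a defect in a stated decision rule. As written, the exception returns indirectly drug-caused Grade 3 or higher anemia to the DLT count and leaves directly caused anemia out. The threshold meaning is probably intended, but the protocol does not state it.

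What is certain is that one reclassified subject can change a 3+3 decision. How much this matters in practice cannot be derived from the document. It is nil if the threshold reading is already applied. The top of the illustrative range, 37 points, should not be read as an estimate: it needs a 20% rate of direct severe anemia in Cycle 1, the literal reading applied every time, and no capture by any other row. The case for correction rests on the wording and the 3+3 rules, not on those figures. It should be fixed, with medium confidence about its consequence.

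**What to change.** After confirming the intent against the source-language text, change the anemia exception in the note to Table 4 to *unless related to MRG003 (directly or indirectly)*. Then list any Grade 3 or higher anemia in cohorts already assessed and check how each case was classified. If none was left out under the literal wording, nothing more is needed.

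The cost is one phrase by amendment and a short look-up, with no new procedures. The downside is that each severe anemia must be attributed, which is harder in patients who enter near the 9 g/dL hemoglobin limit (7.3), and escalation may stop earlier than it would if such cases were left out.
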